3.2.1 Breast Cancer Use case

Objective. The measures described below have no scientific rationale; their intent is to demonstrate that heterogenous data curated across different sites and different countries have been "FAIRified" thanks to AIDAVA i.e. they can produce comparable - and interoperable - data sets across different sites, supporting de facto delivery of a federated cross site registry.

The metrics will be based on assessing time needed and accuracy for 3 queries to be performed on the BC registry. **Important to note that the queries need to have a consolidated answer ACROSS sites** to demonstrate interoperability.

Queries	Technical Specification of the query (all codes are SNOMED code
	matched with the list of Data Elements in the BC registry)
Metric 1: Percentage of patients	BC1 = P2/P1 WHERE
- across sites -  treated with	
breast conserving therapy and	P1 = Total number of patients 404684003 Clinical finding (finding)
whole breast radiotherapy that	WITH 64368001 Excision of part of breast (procedure)
receive a boost to the tumour	AND 428923005 Radiotherapy to breast (procedure)
bed.	
	P2 = Total number of patients 404684003 Clinical finding (finding)
	WITH 64368001 Excision of part of breast (procedure)
	AND 428923005 Radiotherapy to breast (procedure)
	AND 445232009 Boost radiation therapy (procedure)
Metric 2: Percentage of patients	BC2 = P2/P1 WHERE
- across sites - undergoing	
breast surgery and	P1 = Total number of patients 404684003 Clinical finding (finding)
radiotherapy, without adjuvant	WITH 392090004 Operation on breast (procedure)
chemotherapy AND with time	AND 108290001 Radiotherapy (procedure)
between surgery and	WITHOUT 367336001 Chemotherapy (procedure)
radiotherapy > 8 weeks	BEGINTIME OF (367336001 Chemotherapy (procedure))
	>=
	BEGINTIME OF (392090004 Operation on breast
	(procedure))
	P2 = Total number of patients 404684003 Clinical finding (finding)
	WITH 392090004 Operation on breast (procedure)
	AND 108290001 Radiotherapy (procedure)
	WITHOUT 367336001 [Chemotherapy (procedure)]
	BEGINTIME OF (367336001 Chemotherapy (procedure))
	>=
	BEGINTIME OF (392090004 Operation on breast
	(procedure)))
	AND TIME OF 108290001 kadiotherapy (procedure)
	7- TIME of (108290001 Radiotherapy (procedure) + 8 weeks)
Metric 3: Percentage of in	BC3 = P2/P1 WHERE

Queries	Technical Specification of the query (all codes are SNOMED code matched with the list of Data Elements in the BC registry)

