3.2.2 Cardiovascular Use case

Objective. The objective of the endpoints below is to demonstrate the value of having interoperable and reusable data in a standard format to generate valuable and high-quality information in clinical care, without additional burden to the treating physicians.

Objective	(Secondary) end point
Metric 1. Compare scoring time	Metric definition: Time to compute the SMART score (see
between AIDAVA and CVD	definition below)
expert	
	Measurement:

Objective	(Secondary) end point	
	TCVD. Time required for the treating physician to compute the SMART risk score (collect + analyse + enter data into a standalone web page calculator) - per estimate of user in dedicated entry form - compared to the time needed to calculate the same score by AIDAVA, automatically (G1 and G2)	
Metric 2: Compare scoring accuracy between AIDAVA and CVD expert	Metric definition: Accuracy of automatic calculation of the U-Prevent SMART risk score compared to cardiovascular expert-entered score calculation (% difference in the score output - per estimate of user in dedicated entry form) (G1 and G2)	
	 Measurement: CVD1. U-Prevent SMART score computed by treating physician (https://u-prevent.com/calculators/smartScore) CVD2. U-Prevent SMART score computed by AIDAVA 	

The SMART Risk Score [4] is a tool to estimate 10-year risk for recurrent vascular events in patients with manifest cardiovascular disease. The calculator is located at the U-Prevent site [5], a clinical decision support platform, for the application of risk prediction models in clinical practice; the calculator has been recreated and optimised by ORTEC for personalised cardiovascular risk management. The U-Prevent site is CE marked according to the Medical Devices Directives (MDD); marking for MDR compliance is in progress. The pilot site was built by UMC Utrecht. Using the calculators is free. The U-Prevent team develops extra services for premium users, optimization of data management, e.g. by FAIR and GDPR-compliant data exchange from electronic health records. Technical specification to compute Model A, the SMART Risk Score [6] can be found below.

Formulas	SNOMED / LOINC Code (available in PHKG)	Population ¹² value if missing
Recalibrated SMART risk score for	patients with CVD:	
10-year cardiovascular disease risk	: (%) = (1- 0.71840 exp[A + 1.933]) x 100%	
where A =		
-0.0349602236 x age in years	Compute from SNOMED: 184099003 Date of birth	Mandatory

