9.1 Statistical Hypotheses

The primary objective is to demonstrate that G1 of the AIDAVA prototype is superior to the current situation in achieving data curation and publishing of personal health data; and that G2 is superior to G1. Improved efficiency will be measured through 4 endpoints i.e. M1 (usability of the tool), M2 (decreased time to curated data), M3 (high quality of resulting data), M4 (extraction of structured data from text).

- The 2 critical metrics are M2 (time) and M3 (quality).
- While important, **M1 (usability)** should be possible to improve (more training, increased explanation, ..) and the results of the evaluation will provide directions on how to improve.
- M4 (NLP performance) will improve with the introduction of new technologies (Large Language Models like ChatGPT and BARD) and is therefore less critical for the future of AIDAVA.

Thus, the null hypothesis to be tested in relation to the **primary estimand**¹⁷ is as follows.

• Null hypothesis (H0): The efficiency of data curation and publishing of personal health data is not different between G1 or G2 of the AIDAVA prototype and the current situation. There is no impact due to training on data curation.

vs.

- Alternative hypothesis (H1):
 - G1 of the AIDAVA prototype is more effective than the current situation with respect to the efficiency of data curation and publishing of personal health data and G2 is even more effective than G1.
 - The efficiency improvement is due mainly to the tool; some improvement is related to the training on data curation.

The null and alternative hypotheses corresponding to the secondary estimands are as follows:

Secondary objective for Breast Cancer Use Case:

- Null hypothesis: There is no difference with AIDAVA, to get an answer to specific queries on the BC registry across sites, in terms of accuracy and time.
- Alternative hypothesis (H2-BC): AIDAVA G1 provides correct answers on queries on the BC registries across sites (with an accuracy 90% or higher), while avoiding BC specialists (and supporting team) to spend time. G2 has similar or better results.

¹⁷ estimand (trial objective) is the target of estimation. In AIDAVA, the primary estimand is improved efficiency in data curation

Secondary objective for CVD specialists :

- Null hypothesis: There is no difference to compute SMART score for patients across sites, in terms of accuracy and time with AIDAVA.

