- Alternative hypothesis (H2 CVD): AIDAVA G1 provides an accurate SMART score (accuracy of 80%+) on patients, across sites, without any time spent by CVD specialists. G2 has similar or better results.

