SDPO	GO	With ± 15 patients on site	 EBCx: estimated total effort (person min, person hours or person days) for BC specialist and supporting local team to answer the queries (BC1, BC2, BC3 described in Section 3.2.1) across sites TBCx: estimated duration (min, hours or days) for the BC specialist to have an answer to the queries (BC1, BC2, BC3) across sites. Duration = time between the first request and the time the answer is provider 		
SDP1	G1	All patients	 EBCx: total effort for BC specialist (and local team) to answer the queries (BC1, BC2, BC3) across sites TBCx: duration (min, hours or days) for the BC specialist to have an answer to the queries (BC1, BC2, BC3) across sites. HBCx: answer to the query as provided by human BC specialist ABCx: answer to the query as computed by AIDAVA ACCx: accuracy of calculation by AIDAVA compared to BC specialist 		
SDP2	G2		Same than SDP1 - for G2		
		1	CVD		
SDP1	G1	All patients	 CVD. SMART risk score computed by AIDAVA TCVD1.1/TCVD1.2. Time required for the treating/ senior physician to compute the SMART score (collect + analyse + enter data into a standalone web page calculator) CVD1.1/CVD1.2. SMART score computed by treating / senior physician ACVD1.1/ACVD1.2. Accuracy of automatic calculation of the score compared to treating/senior physician-entered score 		
SDP2	G2		Same than SDP1 - for G2		

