A1	Sum across patient arms for G1 A1.M1 = M1@PDP4 + M1@PDP6 A1.M2.x = M2.x@PDP4 + M2.x@PDP6 A1.M3.x = M3.x@PDP4 + M3.x@PDP6 A1.M4.x = M4.x@PDP4 + M4.x@PDP6	Descriptive Statistics Performance in G1 of the AIDAVA system.			
A2	Sum across patient arms for G2	Descriptive Statistics			

Computed	Description of measures	Test & meaning (per H1)
	A2.M1 = M1@PDP5 + M1@PDP7 A2.M2.x = M2.x@PDP5 + M2.x@PDP7 A2.M3.x = M3.x@PDP5 + M3.x@PDP7 A2.M4.x = M4.1@PDP5 + M4.x@PDP7	Performance in G2 of the AIDAVA system.
A3	Difference in A1 and A2 (i.e. difference between G1 and G2 across all patients)	Unpaired t-test
	Α3.Μ1-Δ = Α1.Μ1 - Α2.Μ1	H1: G2 more usable than G1
	A3.M2.xΔ = A1.M2.x - A2.M2.x A3.M3.x-Δ = A1.M3.x - A2.M3.x	H1: G2 requires less time for curation than G1 H1: G2 enable curation with less human intervention than G1
	A3.M4.X-∆ = A1.M4.x - A2.M4.x	Wilcoxon signed-rank test H1: The NLP system developed in G2 yields a higher precision than the NLP system from G1. H1: The NLP system developed in G2 yields a higher recall than the NLP system from G1.
A4	Difference in P1 and P2 (difference between the 2 patient arms)	Unpaired t-test (effect on training/experience) There is a difference in performance due to training/experience with the system : patients having used G1 are more/not more effective in G2 than patients who work with only one generation of the prototype (G1 or G2)
	Α4.Μ1-Δ = P1.Μ1-Δ - P2.Μ1-Δ	H1: G2 more usable than G1 (due to experience during G1)
	A4.M2.x-Δ = P1.M2.x-Δ - P2.M2.x-Δ A4.M3.x-Δ = P1.M3.x-Δ - P2.M3.x-Δ	H1: G2 requires less time for curation than G1 as patients are more experienced H1: There are less questions of the system unanswered during G2 than in G1 as the patient acquired experience in G1
	A4.M4	Not useful

Secondary Endpoint(s) Analysis

Description of measures	Test & meaning (per H1)
Breast Canc	er
Difference in data points 0 and 1 (i.e. difference between G0 and G1 across a sample of 15 patients) U0.TBCx- Δ = TBCx@SDP0 - TBCx@SDPA U0.EBCx- Δ = EBCx@SDP0 - EBCx@SDP1 U0.ACCx- Δ = ACCx@SDP0 - ACCx@SDP1	Unpaired t-test H1: G2 has more (or same) accuracy than G1 while keeping the same time saving and duration
	Descriptive Statistics around performance in G1 of the AIDAVA system (e.g. mean,)

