Difference in data points 1 and 2 (i.e. difference between G1 and G2 across all patients) U1.TBCx- Δ = TBCx@SDP1 - TBCx@SDP2 U1.EBCx- Δ = EBCx@PSP1 - EBCx@SDP2 U1.ACCx- Δ = ACCx@SDP1 - ACCx@SDP2	Paired t-test H1: G2 has more (or same) accuracy than G1 while keeping the same time saving and duration
Cardiovascu	lar
	Descriptive Statistics around performance in G1 of the AIDAVA system (e.g. mean,)
Difference in data points 1 and 2 (i.e. difference between G1 and G2 across all patients) U1.TCVD- Δ = TCVD@SDP1 - TCVD@SDP2	Paired t-test H1: G2 has more (or same) accuracy than G1 while keeping the same time saving
	Description of measures Breast Canc Difference in data points 0 and 1 (i.e. difference between G0 and G1 across a sample of 15 patients) U0.TBCx- Δ = TBCx@SDP0 - TBCx@SDPA U0.EBCx- Δ = EBCx@SDP0 - EBCx@SDP1 U0.ACCx- Δ = ACCx@SDP0 - ACCx@SDP1 Difference in data points 1 and 2 (i.e. difference between G1 and G2 across all patients) U1.TBCx- Δ = TBCx@SDP1 - TBCx@SDP2 U1.EBCx- Δ = EBCx@PSP1 - EBCx@SDP2 U1.ACCx- Δ = ACCx@SDP1 - ACCx@SDP2 Cardiovascu Difference in data points 1 and 2 (i.e. difference between G1 and G2 across all patients) U1.TCVD- Δ = TCVD@SDP1 - TCVD@SDP2 U1.ACCyD- Δ = ACVD@SDP1 - ACVD@SDP2 U1.ACCyD- Δ = ACVD@SDP1 - ACVD@SDP2

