10.3.4 Data user/consumers spreadsheet: Breast Cancer Specialist and CVD clinicians

Breast Cancer

Form to be used by the Breast Cancer Specialist to enter time related to management of the BC registry

Breast Cancer Specialist - Data User Form - G0	
Site name:	 NEMC - Sihtasutus Põhja-Eesti Regionaalhaigla UM - Maastricht University MUG - Medizinische Universität Graz
Data User ID / pseudonym:	✓
To be computed for 45 patients across sites (15 patients in your own site + time to get info on 30 patients in t	he other 2 sites)
TBC1. Estimated time to compute the percentage of patients - across sites - treated with breast conserving therapy and whole breast radiotherapy that receive a boost to the tumour bed without AIDAVA (in min):	(example: 2 or 6 or)
TBC2. Estimated time to compute the number of patients - across sites - undergoing surgery and radiotherapy, without adjuvant chemotherapy: % of patients with time between surgery and radiotherapy > 8 weeks without AIDAVA (in min):	(example: 2 or 6 or)
TBC3. Estimated time to compute the number of patients - across sites - receiving radiotherapy: Percentage of patients receiving any nodal radiotherapy without AIDAVA (in min):	(example: 2 or 6 or)

This form is linked with a table that contains all the metrics manually entered in REDCap (as .csv-export) that are needed to evaluate the system from a BC specialist perspective.

Breast			G1				G2	
Cancer	BC1	BC2	BC3	Comments	BC1	BC2	BC3	Comments
NEMC								
MUG								
Maastro								
MEAN								
MEDIAN								

CVD specialist

Form to be used by the CVD specialist to enter the manually computed SMArt score and the time needed to compute this form manually

CVD Specialist - Data User Form - G1 & G2	
Generation of the prototype	 B O Generation 1 C Generation 2 reset
Site name:	 NEMC - Sihtasutus Põhja-Eesti Regionaalhaigla UM - Maastricht University MUG - Medizinische Universität Graz
Data User ID / pseudonym:	~
Patient ID / pseudonym:	
Date:	H Today Y-M-D
CVD1. SMART risk score computed by the physician(s) for the patient (from this site): U-prevent SMART risk score calculator	SMART risk score computed by CVD Specialist SMART risk score computed by another person Name of this other person
TCVD1. Time required for the treating physician to compute the SMART risk score (collect + analyze + enter data into a standalone web page calculator) in min:	(example: 10 or 20 or)

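### The breast cancer accuracy t-tests in section 9.3 cannot be run as written, and no listed test addresses the 90% (BC) or 80% (CVD) accuracy threshold

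*Protocol*

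**What the plan says.** Section 9.1 sets two secondary hypotheses about G1. For breast cancer, AIDAVA "provides correct answers on queries on the BC registries across sites (with an accuracy 90% or higher"). For cardiovascular disease, "AIDAVA G1 provides an accurate SMART score (accuracy of 80%+) on patients". In both, G2 is expected to do as well or better.

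Section 3.2.1 defines BC accuracy for each of three queries as AIDAVA's value compared with the specialist's. Each query returns a percentage, and the section stresses: "Important to note that the queries need to have a consolidated answer ACROSS sites". Section 3.2.2 defines CVD accuracy as a percentage "difference in the score output - per estimate of user in dedicated entry form".

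Section 9.3 then lists the tests:
- U0 (BC, G0 against G1), unpaired t-test, including "ACCx@SDP0 - ACCx@SDP1". The hypothesis printed in this row concerns G2 against G1.
- U1 (BC, G1 against G2, described as covering all patients), paired t-test, including "ACCx@SDP1 - ACCx@SDP2".
- U1 (CVD, G1 against G2, also described as covering all patients), paired t-test on time and accuracy.
- Descriptive statistics on G1 performance for both use cases.

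In section 9.2, SDP0, the BC data point at G0, is described as "With ± 15 patients on site" and lists only effort and duration. The G0 form in section 10.3.4 asks only for times, "To be computed for 45 patients across sites".

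**The concern.** The tests named in section 9.3 do not match the data that sections 3.2, 9.2 and 10.3.4 provide. One BC contrast needs a quantity that is never collected. The other asks for a patient-level paired test on a figure that exists once per query and generation. Both hypotheses state an absolute accuracy level at G1, while every listed accuracy test is a difference between generations. The stated aim that G2 has more or the same accuracy would in practice be read from a non-significant t-test, which does not show sameness.

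At stake is whether the two explicit secondary hypotheses get a formal answer from the planned analysis. This is more than detail left to a later analysis plan: the protocol itself fixes these tests and data points.

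**Working it through.** The protocol gives no power calculation, significance level or sidedness for these hypotheses, so there is no figure of its own to reproduce. Two-sided 5% is assumed below. The only planning arithmetic is 3 sites × 15 patients = 45 per use case, which agrees with section 9.4.

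**1. BC, G0 against G1.** Accuracy needs AIDAVA's value and the specialist's value. At G0 there is no AIDAVA, SDP0 lists neither value, and the G0 form collects neither. Observations at G0: 0. The contrast cannot be computed. The effort and duration contrasts in the same row do have G0 data.

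**2. BC, G1 against G2.** Count the pairs per query.
- Consolidated answer: 1 pair, df = 1 − 1 = 0. The t statistic and p-value are undefined.
- Three site rows, as in the results table of section 10.3.4: 3 pairs, df = 2, critical |t| = 4.30. Significance needs a mean difference above 4.303/√3 = 2.48 SD. With a non-central t distribution (df = 2, non-centrality d√3), power reaches 80% at d = 3.26 SD.

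**3. Thresholds.** The listed statistic is accuracy at G1 minus accuracy at G2. It is zero for 60% against 60% and for 95% against 95%, so it carries no information about 90% or 80%. Treating each query as correct or not does not help: if the true rate were exactly 90%, three of three correct would occur with probability 0.90³ = 0.729, and nine of nine (three queries at three sites) with 0.90⁹ = 0.387. No query-level result can show 90%.

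**4. CVD, G1 against G2.** The CVD form carries a patient identifier and a physician score per patient, and there is no G0 term. The paired test therefore runs on patients seen in both generations. The effect detectable at 80% power is 0.43 SD with 45 returning patients, 0.53 SD with 30 and 0.63 SD with 22 (return numbers are assumptions). It cannot cover all patients, because those who use a single generation have no pair.

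**5. What a patient-level BC analysis could show.** Use the exact (Clopper-Pearson) two-sided 95% lower limit with n = 45.
- 45/45: 0.025^(1/45) = 92.1%.
- 44/45: the 2.5% quantile of Beta(44, 2) = 88.2%.

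Only full agreement clears 90%. If true agreement is 95%, that happens with probability 0.95⁴⁵ = 0.10; at 98%, with 0.98⁴⁵ = 0.40. For a query whose denominator holds fewer than 45 patients, full agreement clears 90% only if n > ln 0.025 / ln 0.90 = 35.01, that is, from 36 patients.

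**The case against.** The strongest reply is that this is a proof-of-concept study. Section 3.2.1 itself says the BC measures lack a scientific rationale and serve to demonstrate interoperability. G1 descriptive statistics are planned for both use cases, so observed accuracy can be set beside 90% or 80%. An accuracy formula and an interval could follow in an analysis plan. The staff form has room for two BC specialists per site, so up to six entries per query are conceivable: df = 5 and about 1.43 SD detectable.

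Part of this stands. Because of the descriptive statistics, a reader who infers that the two hypotheses can be neither confirmed nor refuted goes too far; an informal comparison is possible. But it is only informal, and it does not repair tests that the protocol has already fixed. Six entries would still be a comparison among raters of one cohort figure, with no patient-level information.

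Other stronger readings are also unsupported:
- That the CVD test shares the BC defects. CVD scores are per patient and involve no G0 value.
- That the BC time saving is distorted because G0 uses 15 patients and G1 uses 45. About 15 on site and 45 across sites are compatible statements, and U0 describes its whole contrast as covering a sample of 15. The wording needs one patient set; a distortion is not established.
- That the CVD percentage difference is signed, or that the same specialists answer at G0 and G1. The protocol says neither.

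**Conclusion.** The point holds for BC as a defect in the stated tests: the G0-G1 accuracy contrast has no G0 data, and the G1-G2 contrast has 0 degrees of freedom, or 2 with 80% power only at 3.26 SD if site rows count. For both use cases no listed test addresses the 90% or 80% threshold, and a non-significant G1-G2 difference would not establish more or the same accuracy. For CVD the paired test is valid in returning patients but does not answer the 80% hypothesis.

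The power figures rest on an assumed two-sided 5% level. The counts rest on the protocol's requirement for one consolidated answer per query. These are secondary endpoints, so the plan should be corrected, but the primary comparison is not affected.

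**What to change.** - **U0:** delete the accuracy contrast. Correct the row's hypothesis so that it concerns G0 against G1. State one patient set for time and effort, since section 9.3 speaks of a sample of 15 and the G0 form of 45 across sites.
- **BC at G1:** have each site record, per patient and query, whether AIDAVA and the specialist agree on the classification that decides the query (P2 membership among patients in P1). Send only counts across sites, which keeps the federated design. Report agreement with an exact two-sided 95% confidence interval against 90%. Patient-level agreement also reveals errors that would cancel in a cohort percentage.
- **BC, G1 against G2:** replace the t-test by a confidence interval for the difference in agreement, paired in returning patients.
- **CVD at G1:** define accuracy per patient as 100% minus the absolute percentage difference between the AIDAVA and physician scores, and say whether the treating or the senior physician is the reference. Report the mean with a 95% confidence interval against 80%.
- **CVD, G1 against G2:** restrict the paired comparison to returning patients and report a confidence interval, so that sameness is not inferred from non-significance.

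The cost is a short per-patient agreement list at each site, which the protocol does not now ask for, and revised wording in sections 9.1 to 9.3. The intervals will be wide, and for BC a formal claim of 90% will often be out of reach at this sample size. It is better to say so in advance.

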9.4 Sample Size Determination

We expect a minimum of 15 patients per site and per use case, for a total of 90 patients and 12 data curators across the 2 use cases.

The main objective of the study is to assess performance and acceptance of the AIDAVA prototype and provide evidence that the overarching approach - and underlying tools - can open to new possibilities in data quality enhancement and FAIRification of the data. For this proof of concept study, it is assumed that between 50 to 80 subjects will be sufficient. As we expect some drop out between the 2 epochs of the study, for G1 and for G2 of the prototype, we targeted a higher number than needed.

	Use case 1 Health record of cardiac patients	Use case 2 Breast Cancer Patient registry		
NEMC -	15 patients	15 patients		
MIDATA	+3 expert data curators			
MedUniGraz -	15 patients	15 patients		
MIDATA	+3 expert data curators			
MUMC+/Maastro -	15 patients (MUMC)	15 patients (Maastro)		
DIGI.me	+3 expert data curators			
TOTAL	45 patients	45 patients		
	+ 9 expert data curators			

10. Supporting Documentation and Operational Considerations

